## Study protocol

Constipation is a common problem in adult population. Constipation may also lead to pelvic floor muscle dysfunction due to prolonged stress on the pelvic floor. The recommended initial treatment for constipation includes lifestyle modifications (e.g., increasing physical activity, balanced diet) and laxatives. Pelvic floor muscle training (PFMT) with biofeedback has been recognized as an effective therapy for relieving constipation in patients who have failed initial treatment. Since constipation is a multifactorial disorder, a multimodal intervention program may be more effective than single treatment in solving constipation problem^4. However, there is no research investigating the effects of a multimodal exercise training on pelvic floor symptoms and pelvic floor muscle function in this population and only few studies have evaluated the pelvic floor muscle function using objective assessment tools among this population. This study aims to evaluate the effectiveness of a multimodal exercise training program on constipation symptoms and pelvic floor muscle function in adults with constipation.

This is a randomized controlled trial. Adults with functional constipation will be recruited and randomly assigned to two groups, the intervention group, or the control group. The intervention group will receive 16 sessions of physical therapist supervised, combined resistance (including PFMT) and aerobic exercise training twice weekly for 8 weeks, and home exercises (PFMT and walking). The control group will receive only one session of usual care after baseline assessment.

Assessments will be performed at baseline and after eight-week program. The primary outcome measure is the severity of patient's self-reported constipation symptoms. The secondary outcome measures include the pelvic floor muscle function, physical activity levels, constipation-related quality of life, and 7-day bowel chart will also be collected. Moreover, adherence will be calculated separately for PFMT and walking

as the days of home exercises completed over 56 days in intervention group.

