## Statistical analysis plan

Intention-to-treat analysis will be performed to preserve the sample size and original randomization. For participants who have a missing outcome in baseline assessment, the outcome value will be estimated through calculating mean and mode from the existing data. For those who have a missing outcome in post-intervention assessment, the observation from baseline assessment will be carried forward. Shapiro-Wilk test will be used to evaluate the normality of data. Descriptive data will be presented as number, percentage, mean and standard deviation (SD). Mann-Whitney U test and Chi-square test will be used for continuous data and categorical data to compare the baseline characteristics between two groups. Wilcoxon signed rank test and the Mann-Whitney U test will be used for intragroup and intergroup comparison of outcome variables. The p-value of < 0.05 will be considered as statistically significant. All data analyses will be performed using SPSS software version 25.0.

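### The outcome list and SAP include no adverse events, reasons for stopping or harms summary, so the trial can report benefit but cannot report comparable information on harm

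*Combined protocol and SAP*

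**What the plan says.** The Study protocol section names the primary outcome: "The primary outcome measure is the severity of patient's self-reported constipation symptoms". It then gives the remaining measures: "The secondary outcome measures include the pelvic floor muscle function, physical activity levels, constipation-related quality of life, and 7-day bowel chart will also be collected". Adherence to home exercise is added for one arm only, counted "as the days of home exercises completed over 56 days in intervention group".

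On contact with participants, the same section states: "The intervention group will receive 16 sessions of physical therapist supervised, combined resistance (including PFMT) and aerobic exercise training twice weekly for 8 weeks". For the comparator: "The control group will receive only one session of usual care after baseline assessment". On measurement: "Assessments will be performed at baseline and after eight-week program". No restriction by arm is attached to the assessments, so both arms are taken to attend both.

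The Statistical analysis plan compares outcomes as follows: "Wilcoxon signed rank test and the Mann-Whitney U test will be used for intragroup and intergroup comparison of outcome variables". It also says that a missing post-intervention value is replaced by the same participant's baseline value. It gives no adverse-event definition, safety population, harms table or summary of reasons for stopping.

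**The concern.** The Study protocol section justifies the trial partly by saying that multimodal exercise training has not been studied in this population for its effects on pelvic floor symptoms and muscle function. A first trial of such a programme is where readers will look for what went wrong as well as what improved. None of the listed measures would identify pain, injury, cardiovascular symptoms or new urinary or prolapse symptoms in an individual. Group summaries of constipation severity or muscle function cannot stand in for these.

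The missing-data rule adds to the problem. Someone who leaves because of a harm and does not return looks the same in the analysis as someone who simply lost interest.

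The gap is also hard to repair afterwards. If events are only noted informally when participants happen to be seen, the opportunities to note them lie almost entirely in one arm. A two-arm harms record that was not collected prospectively cannot be reconstructed from such notes.

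**Working it through.** The plan gives no sample size, event rate or harms figure, so there is no stated result to reproduce. The check compares the texts, counts contacts and applies the missing-data rule.

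**1. What is collected, and what would show a harm**

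| Item in the Study protocol section | Arms | Identifies an adverse event or reason for stopping? |
|---|---|---|
| Constipation severity (primary) | both | No |
| Pelvic floor muscle function | both | Not as an event; a group deterioration could appear |
| Physical activity | both | No |
| Constipation-related quality of life | both | No |
| 7-day bowel chart | both | No; could show worsening bowel habit |
| Home-exercise adherence | intervention only | No; shows that exercise was not done, not why |

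The Statistical analysis plan adds tests on these outcome variables and nothing on harms.

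**2. Contacts at which a harm could come to light** (all inputs from the Study protocol section)

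- Intervention sessions: 2 per week × 8 weeks = 16, matching the stated 16.
- Adherence window: 8 weeks × 7 days = 56 days, matching the stated 56.
- Control sessions: 1, after baseline.
- Assessments: 2 in each arm.
- All contacts: 16 + 2 = 18 against 1 + 2 = 3, a ratio of 6 to 1.
- Stated contacts after the control session, taking that session to precede training: 16 + 1 = 17 against 1.

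The 6-to-1 figure includes the baseline assessment, which cannot capture events arising during the programme. The last line is the relevant one: the control arm has a single later contact, the final assessment.

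**3. The carry-forward rule applied to someone who stops because of harm**

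Change = post-intervention value − baseline value. If the post-intervention value is missing, it is set to the baseline value, so change = baseline − baseline = 0. The result is the same whatever the reason for stopping, and no reason is recorded.

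**4. Can the size of a detection imbalance be derived?**

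Let r be a true event risk common to both arms, and c₁ and c₀ the fractions of events captured in the intervention and control arms. The recorded risk ratio is (r × c₁) / (r × c₀) = c₁ / c₀. The true risk cancels, so the ratio is simply whatever capture fractions one assumes. With c₁ = 80% (assumed), c₀ = 60% gives 80/60 = 1.33 and c₀ = 20% gives 80/20 = 4.0. The documents give neither fraction, so the direction is plausible and the size is not determined.

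**The case against.** The strongest reply is that the plan contains no biased harms comparison, because it contains no harms comparison at all. That is correct. A reader might infer that the trial will make exercise look more harmful than it is, perhaps by a ratio such as 1.3 to 4.0. The documents do not support this. It would take unplanned recording followed by an unplanned between-arm comparison, and the ratio only restates assumed capture fractions. What stands is narrower: informal notes, if used, would not be a fair basis for comparison.

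A reader might also take this sentence as the protocol's own warning about exercise: "Constipation may also lead to pelvic floor muscle dysfunction due to prolonged stress on the pelvic floor". Its subject is constipation, which participants in both arms have, so it is no evidence that the programme is harmful.

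It might further be said that worsening in the control arm goes unseen. Both arms are assessed after eight weeks, so deterioration in constipation, bowel habit, quality of life or muscle function would appear then. A form at that same visit does not shorten the interval.

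Finally, the document is brief, part of it was removed before review, and its secondary outcome list is not worded as exhaustive. One cannot conclude that no harm will be recorded anywhere. One can say that the visible outcome list and analysis plan describe no such collection, and a harms report cannot be planned from them.

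**Conclusion.** The concern holds as an omission. The visible plan collects and analyses no adverse events and no reasons for discontinuation, so it supports a conclusion about effectiveness and none about harms. The carry-forward rule scores a participant who leaves because of harm and misses the final assessment as unchanged.

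The contact schedule, 17 stated contacts against 1 after the control session, means that informally noted events could not be compared fairly between arms. The size of that imbalance is unknown. The count assumes that both arms attend the final assessment and that no unstated contacts occur.

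The omission does not invalidate the planned primary comparison. It is an inexpensive improvement that should be made because it changes what the trial can report, but it is not a fault that stops the trial from answering its main question.

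**What to change.** **Study protocol section.** Add to the existing post-intervention assessment, in both arms, one identical prompted checklist covering the preceding 8 weeks. It should ask about adverse events (for example new or worse pain, injury or falls, new urinary, bowel or prolapse symptoms, cardiovascular symptoms, and unplanned medical care for constipation) and the reason for any discontinuation. The investigators should settle the items. Put the same questions by telephone to participants who withdraw.

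**Statistical analysis plan.** Report by arm, from this checklist only, the number and percentage of participants with at least one event, with the number who answered as denominator and the number who did not shown beside it. Tabulate reasons for discontinuation by arm. List events noted at supervised sessions separately, for the intervention arm alone, and state that they are not compared with control.

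**Cost.** One short form at a visit that already takes place, one table, and a call to those who withdraw: a few minutes per participant and no extra visit, assessor or procedure. The limitation should be stated in the plan. Participants will know their allocation from what they receive, and the intervention arm will have had far more therapist contact, so recall over 8 weeks may still differ by arm. An identical form reduces unequal enquiry but does not remove that difference.

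### Does the plan need an attendance measure for the supervised sessions, given that adherence is defined only for home exercise?

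*Combined protocol and SAP*

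**What the plan says.** The Study protocol section gives the intervention two parts. The first is "16 sessions of physical therapist supervised, combined resistance (including PFMT) and aerobic exercise training twice weekly for 8 weeks". The second is introduced by "and home exercises (PFMT and walking", with no other home activity listed. The control group has a single usual-care session after baseline.

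One adherence measure is defined: "adherence will be calculated separately for PFMT and walking", and it is counted "as the days of home exercises completed over 56 days in intervention group". The outcome list contains nothing on attendance: "The secondary outcome measures include the pelvic floor muscle function, physical activity levels, constipation-related quality of life, and 7-day bowel chart will also be collected".

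The Statistical analysis plan section does not mention adherence. Its analysis principle is "Intention-to-treat analysis will be performed to preserve the sample size and original randomization", and its descriptive format is "Descriptive data will be presented as number, percentage, mean and standard deviation (SD".

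**The concern.** The rationale in the Study protocol section is that "a multimodal intervention program may be more effective than single treatment in solving constipation problem". A reader of the trial report will therefore want to know how much of each part of the program participants received. The stated adherence measure covers only what is done at home. The protocol's wording implies that the resistance training is wider than PFMT, and that wider part appears only in the description of the supervised sessions. A participant could complete every home day and attend no session, and the two planned adherence figures would not show it. After a null result, poor attendance could not be told apart from an ineffective program; after a positive result, the amount of supervised training behind it would be unknown.

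The denominator raises a second doubt. The documents do not say whether home exercise is expected on the days of supervised sessions. If it is not, 56 is larger than the number of home days asked for, and a fully compliant participant would score below 100%.

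**Working it through.** **Inputs, all from the Study protocol section:** 2 sessions per week; 8 weeks; 16 sessions; an adherence denominator of 56 days.

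**The plan's own figures**

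- Sessions: 2 × 8 = 16, as stated.
- Days: 8 × 7 = 56, as stated.

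Both figures are consistent with an 8-week program.

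**Is attendance captured anywhere?** Three places could hold it.

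1. The adherence definition counts home days only.
2. The outcome list includes physical activity levels, but these are an outcome and do not record who came to a session.
3. The SAP has no compliance or per-protocol analysis.

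Attendance is therefore not stated. That is silence, which differs from a decision not to record it.

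**Does any planned result depend on it?** The SAP specifies Mann-Whitney U tests between groups and Wilcoxon signed rank tests within groups on the outcome variables, under intention to treat. Neither adherence nor attendance enters a test, a covariate or the definition of an analysis set. Adding attendance would leave every planned estimate and p-value as it is.

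**What would attendance show?** Home scores of 56/56 are compatible with any attendance from 0/16 to 16/16, because these are separate quantities; that range is not the size of an error. Each session combines PFMT, other resistance work and aerobic work. A count of sessions attended does not say which of these were completed, so it gives an upper limit on the resistance exercise received and does not verify it.

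**Is the denominator too large?** The answer depends on a home schedule that the documents do not give.

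| Assumed number of home days asked for | Score of a fully compliant participant | Understatement |
|---|---|---|
| All 56 days | 56/56 = 100% | 0 points |
| Session days exempt, sessions on separate days: 56 − 16 = 40 | 40/56 = 71.4% | 16/56 = 28.6 points |
| Illustration, 3 days a week: 3 × 8 = 24 | 24/56 = 42.9% | 32/56 = 57.1 points |

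The figure follows wholly from the assumption chosen, so 28.6 points is one scenario and not an estimate. The protocol lists home exercise apart from the supervised sessions and counts it over the full 8 weeks. Daily home exercise is the natural reading, and under it the formula is exact.

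**The case for a change.** The strongest case for a change is that it costs a sentence or two. A plan that already commits to calculating adherence could name the supervised part as well. Left unstated, the choice whether to report attendance can be made after the results are known, and the single word adherence may be taken to cover the whole program. One further sentence would settle whether session days count as home days, so that a reported 71% could not be read either as full compliance or as a shortfall.

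Part of this stands. The documents state no attendance measure; resistance exercise beyond PFMT is described only for the supervised sessions; and a reader would find sessions attended out of 16 useful. It would also be clearer to call the existing measure home adherence when it is reported.

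The rest carries less weight. Selective reporting matters most where a choice can move a tested result, and here attendance feeds no test. The multimodal rationale does not create a need for component-level data in the analysis: the trial compares the whole program with one session of usual care and has no single-treatment arm, so no planned inference separates the components. The denominator point asks for confirmation of the natural reading and identifies no error.

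**Conclusion.** No change to the plan is called for. The omission is a descriptive detail that analysts can supply sensibly, and filling it would alter no planned result. Its effect on the primary comparison, the secondary comparisons and the significance tests is zero, since adherence enters none of them. A count of sessions out of 16, in the SAP's existing descriptive format, would be a reasonable optional line in the report, provided that it is read as a bound on exposure to resistance exercise.

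The 56-day denominator stands. Its understatement is 0 points if home exercise is expected on all 56 days, and becomes positive only under a reduced schedule that the text does not mention.

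This conclusion rests on two assumptions. The first is that session records are kept, which the documents do not say but which is usual where a therapist supervises each session. The second is that adherence stays descriptive. If it were later used to define a per-protocol set or a dose-response analysis, both attendance and the denominator would need to be specified beforehand.

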## Statistical analysis plan

Intention-to-treat analysis will be performed to preserve the sample size and original randomization. For participants who have a missing outcome in baseline assessment, the outcome value will be estimated through calculating mean and mode from the existing data. For those who have a missing outcome in post-intervention assessment, the observation from baseline assessment will be carried forward. Shapiro-Wilk test will be used to evaluate the normality of data. Descriptive data will be presented as number, percentage, mean and standard deviation (SD). Mann-Whitney U test and Chi-square test will be used for continuous data and categorical data to compare the baseline characteristics between two groups. Wilcoxon signed rank test and the Mann-Whitney U test will be used for intragroup and intergroup comparison of outcome variables. The p-value of < 0.05 will be considered as statistically significant. All data analyses will be performed using SPSS software version 25.0.

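### Missing week-8 outcomes are all filled with the baseline value, with no stated missing-data assumption or sensitivity analysis, and the resulting bias can go either way

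*Combined protocol and SAP*

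**What the plan says.** The Study protocol section schedules two measurements: "Assessments will be performed at baseline and after eight-week program". The primary outcome is self-reported symptom severity. The exercise arm has 16 supervised sessions over eight weeks plus home exercise. For the other arm, "The control group will receive only one session of usual care after baseline assessment".

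The Statistical analysis plan section opens with "Intention-to-treat analysis will be performed to preserve the sample size and original randomization". A missing baseline value is filled by a mean or mode. For follow-up, "For those who have a missing outcome in post-intervention assessment, the observation from baseline assessment will be carried forward". This applies to every outcome, both arms and any reason for loss. The tests follow: "Wilcoxon signed rank test and the Mann-Whitney U test will be used for intragroup and intergroup comparison of outcome variables". The plan does not say whether the between-group test uses post scores or changes. Descriptive results will include means and SDs.

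Neither section names a missing-data mechanism, an alternative analysis, a sensitivity analysis or an expected dropout rate.

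**The concern.** With only two visits, the carried-forward value is always the baseline, so the imputed change is zero by construction. The between-group test and the group means then treat that zero as if it had been measured. Keeping people in their randomised arms does not justify the values written in for them.

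The rule acts on the primary comparison. The arms differ sharply in burden and contact, so unequal loss is plausible. Depending on who leaves and how they fare, the rule can hide part of a real benefit or produce an apparent one. With a single unexplained rule and no sensitivity analysis, a reader of the results could not tell which had happened.

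**Working it through.** **Inputs.** The documents give the rule, the two visits, the tests and the 0.05 level (two-sided assumed). They give no sample size, dropout, SD or expected change, so there is no planned figure to reproduce. Everything below is assumed, in baseline-SD units. Dropout is written intervention/control.

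**Formula.** Let d be the share lost and m the true mean improvement of those lost. Carry-forward replaces m by 0, so the estimated difference minus the true difference is dC×mC − dI×mI. Positive values favour exercise. If dropout is unrelated to outcome, m equals the arm mean and the estimate is mI(1−dI) − mC(1−dC).

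**Dropout unrelated to outcome; true improvement 0.8 v 0.3, difference 0.50.**
- 20%/20%: 0.8×0.80 − 0.3×0.80 = 0.40.
- 25%/10%: 0.8×0.75 − 0.3×0.90 = 0.33. The exercise arm's own mean falls from 0.80 to 0.60.
- 10%/30%: 0.8×0.90 − 0.3×0.70 = 0.51.
- Here the bias turns toward exercise only when control dropout exceeds 0.8/0.3 = 2.67 times exercise dropout.

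**Dropout related to outcome.**
- Suppose exercise completers improve 0.8, those lost from exercise worsen by 0.3, and control improves 0.3 with nobody lost. At 20% exercise loss the truth is 0.8×0.80 − 0.3×0.20 − 0.3 = 0.28. Carry-forward gives 0.64 − 0.3 = 0.34. The rule favours exercise although all the loss is in that arm.
- Suppose instead that below-median improvers leave with probability 1.6d and others with 0.4d (four to one). At baseline–post correlation 0.5 the change has SD 1, so those lost improve by the arm mean minus 0.6×0.798 = 0.479.
  - No mean change, 30%/10%: bias = 0.10×(−0.479) − 0.30×(−0.479) = +0.096.
  - Mean improvement 0.5 in both arms, 30%/10%: those lost improve 0.021, so the bias is (0.10 − 0.30)×0.021 = −0.004, almost nil.

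**Simulation.** Bivariate normal data, 30 per arm, correlation 0.5. There were 20,000 replicates for dropout unrelated to outcome, 10,000 for related dropout, and 3,000 for related dropout with no mean change. Triples are Mann-Whitney on post values; Mann-Whitney on change; baseline-adjusted model.

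| Case | Observed data | Carry-forward |
|---|---|---|
| Power, 0.8 v 0.3, 20%/20%, unrelated | 37; 37; 49% | 30; 34; 44% |
| Power, 0.8 v 0.3, 25%/10%, unrelated | 38; 38; 50% | 22; 22; 31% |
| Two-sided error, both improve 1 SD, 10%/30%, unrelated | 5.1; 4.9; 5.1% | 10.5; 14.8; 14.3% |
| Two-sided error, both improve 0.5 SD, 10%/30%, unrelated | not tabulated | 6.5; 8.1; 7.5% |
| Two-sided error, no mean change, 30%/10%, poorer responders leave | not tabulated | 6.4; 7.4; 8.0% |

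In the last row, false wins for exercise are 5.4%, 6.5% and 7.1% against a nominal 2.5%. Carry-forward error stays near 5% at 20%/20% with 1 SD improvement in both arms (4.8% to 5.0%), and at 10%/30% with no mean change and unrelated dropout (4.7% to 5.1%).

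Over correlations 0.3 to 0.7, the 25%/10% power cost is 16, 12 to 26 and 17 to 24 points.

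**Limits of the alternative.** Take the four-to-one dropout with both arms improving 0.5 at 30%/10%. False exercise wins at 30 and 60 per arm are 6.3% and 9.3% for the adjusted model on observed data, and 6.0% and 9.3% for multiple imputation. A delta of 0.5 SD brings imputation to 2.7% and 3.0%. With a true difference of 0.50 at 25%/10%, carry-forward gives 0.40. Imputation runs from 0.58 (delta 0) through 0.51 (0.5) to 0.43 (1.0).

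**The case against.** **Carry-forward is conservative, and a cautious default is defensible.** Often it is: with dropout unrelated to outcome and an effective programme, it usually shrinks the difference. But that is a property of certain dropout patterns, and the plan does not say which it expects. The opposite inference, that the rule generally favours exercise, is not supported either.

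**If nobody changes on average, filling in baseline is harmless.** A reader might infer this from the benign cases. It holds only if dropout is unrelated to outcome. When poorer responders leave the exercise arm more often, error rises to about 6% to 8%. Likewise, carry-forward's near-nominal behaviour with 0.5 SD improvement is a coincidence of that choice, because those lost then truly change by about zero.

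**The zero is not treated as data everywhere.** This stands in part. The standard Wilcoxon signed rank test drops zero differences, so the within-group test may be less affected. The plan does not say how zeros are handled. The point concerns the between-group comparison and the reported means.

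**Every size is assumed, and the power losses suit the alternative.** This stands. The tabulated power costs assume dropout unrelated to outcome. Under the four-to-one dropout, the errors are similar in size: carry-forward is about 0.10 too low and the adjusted model about 0.08 too high.

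**Stating the assumption and adding a sensitivity analysis would be enough.** That would cure the omission. It would leave the primary estimate resting on zero change for everyone lost, which is why a change of main analysis is also advised.

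**Conclusion.** The concern holds in this form. The plan scores every participant lost to follow-up as zero change in the primary comparison and the group means, and gives neither an assumption nor a sensitivity analysis. High confidence applies to that omission and to the bias formula, because neither depends on an assumed number.

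Direction and size are conditional. If dropout is unrelated to outcome, the rule usually dilutes a true effect, and it favours exercise when control loss is much heavier and both arms improve. If those lost from exercise worsen, it can favour exercise even when exercise loses more. False positives stay near nominal when there is no true difference and dropout is similar in the two arms, or when dropout is unrelated to outcome and nobody changes on average.

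A reader might infer that this trial's result will be biased by a particular amount, or invalid. The documents do not support that, because they give no sample size, dropout or SD. This should be fixed before analysis.

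**What to change.** Name one primary between-group analysis: all randomised participants by arm, within-arm multiple imputation of missing post values from baseline, a baseline-adjusted model, Rubin pooling, and an explicit missing-at-random assumption. Use the same approach for continuous secondary outcomes. Keep the Mann-Whitney test with baseline carry-forward as a supportive sensitivity analysis.

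Add delta-adjusted imputation over a stated range, for example 0 to 1 baseline SD worse. Apply it in both arms and then in the exercise arm alone: a common delta shifts the difference by delta×(dC − dI), which is zero at equal dropout. Report dropout by arm.

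**Cost.** No extra participants, visits or data. The main test changes, because Rubin pooling needs an estimate and a standard error, and there is more analysis work. Missing-at-random cannot be tested with one follow-up visit. It can overstate benefit if poor responders leave the exercise arm more often (about 6% to 9% false exercise wins in the assumed case), so the delta analysis is a required part of the change.

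### The only between-group outcome test is an unadjusted Mann-Whitney U test; the score it compares is not named, and no effect estimate with a confidence interval is planned

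*Combined protocol and SAP*

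**What the plan says.** On timing, the Study protocol section says: "Assessments will be performed at baseline and after eight-week program". On the primary outcome: "The primary outcome measure is the severity of patient's self-reported constipation symptoms". It names neither the instrument nor the form of the score (8-week value or change).

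The Statistical analysis plan gives outcome comparisons one sentence: "Wilcoxon signed rank test and the Mann-Whitney U test will be used for intragroup and intergroup comparison of outcome variables". Read in order, Wilcoxon is the within-group test and Mann-Whitney the between-group test. The only other between-group tests concern baseline: "Mann-Whitney U test and Chi-square test will be used for continuous data and categorical data to compare the baseline characteristics between two groups".

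Apart from the within-group tests, baseline outcome values have one stated role in handling the 8-week result: "For those who have a missing outcome in post-intervention assessment, the observation from baseline assessment will be carried forward". No covariate or adjusted model is named. The planned summaries are counts, percentages, means and SDs, and the decision rule is p < 0.05. The plan also says "Shapiro-Wilk test will be used to evaluate the normality of data", but attaches no consequence to the result.

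**The concern.** The stated purpose is effectiveness: "This study aims to evaluate the effectiveness of a multimodal exercise training program on constipation symptoms". Three features of the analysis work against it.

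- **Precision.** A Mann-Whitney test on 8-week scores ignores the baseline value. A test on change scores uses it, but with a fixed slope of 1, which costs precision when the correlation is low. A baseline-adjusted analysis estimates the slope from the data.
- **Unnamed score.** The 8-week and change versions can give different answers. Which has more power depends on a correlation not known in advance, and an open choice can be settled after the data are seen.
- **No estimate.** Group means with SDs and a p-value do not commit the trial to saying how much symptoms improve relative to control, or how precisely that is known.

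**Working it through.** **Inputs.** From the documents: two randomised groups, one baseline and one 8-week assessment, Mann-Whitney between groups, threshold 0.05. There is no sample-size or power figure to reproduce. Assumed for illustration: a two-sided test, equal arms, 30 per arm, an effect of 0.6 SD, and a baseline-to-8-week correlation (rho) of 0, 0.3, 0.5 or 0.7.

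**Step 1: variance, normal approximation.** Relative to the 8-week score alone, the variance is 2(1 − rho) for a change score and 1 − rho² after baseline adjustment.

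| rho | Change score | Baseline-adjusted |
|---|---|---|
| 0.3 | 1.40 | 0.91 |
| 0.5 | 1.00 | 0.75 |
| 0.7 | 0.60 | 0.51 |

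The number per arm for 80% power is 2(1.960 + 0.842)² × variance ratio / d². At d = 0.5 this gives 63 for the 8-week score; 88, 63 and 38 for change; and 58, 48 and 33 adjusted. The choice between 8-week and change score thus moves the requirement from about 1.4 times to 0.6 times.

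**Step 2: simulated power.** 4,000 runs per cell, so the simulation standard error is at most √(0.25/4000) = 0.8 points. Each cell gives power in % at rho 0 / 0.3 / 0.5 / 0.7. MW is Mann-Whitney.

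| Data | MW, 8-week | MW, change | Rank ANCOVA | Raw-scale linear ANCOVA | Rank ANCOVA minus better MW |
|---|---|---|---|---|---|
| Normal | 59.3 / 59.4 / 59.7 / 60.5 | 34.1 / 45.7 / 58.2 / 81.0 | 59.0 / 62.8 / 70.9 / 85.6 | 61.6 / 65.3 / 74.1 / 88.9 | −0.3 / 3.4 / 11.2 / 4.6 |
| Log-normal, proportional decrease | 60.5 / 59.2 / 59.5 / 60.3 | 29.6 / 38.3 / 51.1 / 71.0 | 60.2 / 63.2 / 71.1 / 84.4 | 55.8 / 60.4 / 67.6 / 82.0 | −0.3 / 4.0 / 11.6 / 13.4 |
| Log-normal, additive shift | 79.0 / 78.6 / 78.9 / 78.4 | 42.7 / 57.3 / 71.3 / 89.5 | 79.3 / 81.7 / 87.7 / 95.7 | 64.1 / 66.8 / 73.8 / 86.3 | 0.3 / 3.1 / 8.8 / 6.2 |
| Five-level ordinal | 56.1 / 57.0 / 56.9 / 56.8 | 31.6 / 40.6 / 49.8 / 67.2 | 56.4 / 60.1 / 66.2 / 78.9 | 56.9 / 60.0 / 66.3 / 78.6 | 0.3 / 3.1 / 9.3 / 11.7 |

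Direction matters. For a proportional increase, change-score power at rho 0.7 is about 82%, so the gain there falls from about 13 points to about 84 − 82 = 2.

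Scale matters too. Under the additive shift, raw-scale linear ANCOVA trails the better Mann-Whitney version at every rho: 64.1 against 79.0, 66.8 against 78.6, 73.8 against 78.9, 86.3 against 89.5. In the proportional case, linear ANCOVA on logs has 61.6 / 65.6 / 74.2 / 87.7%.

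**Step 3: intervals, like for like.** The adjusted Hodges-Lehmann interval is computed on 8-week scores minus the fitted baseline slope times baseline (3,000 runs, normal data, SD units).

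| rho | Unadjusted width, 8-week | Adjusted width | Narrower by |
|---|---|---|---|
| 0.3 | 1.066 | 1.009 | 1 − 1.009/1.066 = 5% |
| 0.5 | 1.061 | 0.914 | 1 − 0.914/1.061 = 14% |
| 0.7 | 1.069 | 0.756 | 1 − 0.756/1.069 = 29% |

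Coverage of the adjusted interval was 94.2% to 95.5% over the normal and log-normal cases; it was not examined for ordinal scores. Its smallest gain in power was 80.4 − 78.6 = 1.8 points (additive skew, rho 0.3).

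**Step 4: validity.** With no effect, the type I error was 4.2% to 5.7% for every method, including both Mann-Whitney versions.

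**The case against.** The strongest reply is that an unadjusted rank test is a legitimate choice in a randomised trial, that it suits skewed or ordinal symptom scores, and that every magnitude above is assumed. Most of this stands. The test is valid, adjustment is a recommendation about efficiency, and at rho near 0 it buys nothing. The simulations also leave out the plan's carry-forward rule. The reply does not touch the unnamed score and the missing estimate, which are facts of the text and do not depend on rho. A rank-based adjusted analysis also meets the point about skew.

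Three stronger readings are tempting and should be resisted.

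- A reader might infer that the unadjusted comparison is biased or inflates false positives. Randomisation and Step 4 say otherwise.
- A reader might infer that both scores will be tested and the better one reported. If that were always done, the type I error on one outcome would be about 8% to 10%, but the plan does not say so and never mentions a change score.
- A reader might infer that adjustment is always superior. It removes the guess about correlation, not the choice of scale, as the additive-shift row shows.

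**Conclusion.** The point holds as one of precision and interpretability. The plan's only between-group outcome test makes no covariate use of a baseline value already collected, does not name its score, and comes with no estimate or interval.

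Under the assumed 30 per arm, 0.6 SD and rho 0.3 to 0.7, rank-based adjustment gains roughly 2 to 13 points of power over the better Mann-Whitney version, depending on data shape and direction of effect. On normal data its interval is about 5%, 14% and 29% narrower than the unadjusted 8-week interval at rho 0.3, 0.5 and 0.7. None of these figures describes this trial, because the documents supply no sample size, SD, correlation or instrument. The change is worth making because it needs no new data, not because the planned test is wrong.

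**What to change.** Before data are seen, amend the Statistical analysis plan as follows.

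1. For the primary outcome and each continuous secondary outcome, make the main comparison a baseline-adjusted analysis of the 8-week score on arm and the baseline score of the same outcome. Report the adjusted difference with its 95% CI.
2. If skewed or ordinal scores are expected, use either a rank-based adjusted analysis with its computation stated, or linear ANCOVA on a pre-specified transformed scale. An example of the former is Mann-Whitney with its Hodges-Lehmann interval on 8-week scores minus the fitted baseline slope times baseline, so that test and interval agree. Use raw-scale linear ANCOVA only if scores are expected to be roughly normal.
3. Fix the method in advance, not from the Shapiro-Wilk result.
4. Keep Mann-Whitney on a named score, with its Hodges-Lehmann difference and 95% CI, as a sensitivity analysis, and state that the main analysis decides.
5. If Mann-Whitney stays as the main test, the minimum repair is to name the score and report that difference and interval.

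**Cost.** SAP wording, slightly more analysis work and one choice to fix in advance. Choosing rank ANCOVA when data turn out normal gives up about 3 points of power against linear ANCOVA (for example 74.1 − 70.9 = 3.2 at rho 0.5). Main and sensitivity tests can also disagree: rank ANCOVA and Mann-Whitney on 8-week scores differed on significance in about 10%, 17% and 28% of simulated trials at rho 0.3, 0.5 and 0.7, which is why item 4 must name the deciding analysis.
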